	• Comparison of centralized, blinded pathologic assessment to local pathologic assessment of the excised lymph node(s) to confirm the presence/absence of tumor metastases on a per-subject and per-node basis
	• False negative rates and sensitivity for each detection method in subjects undergoing lymphadenectomy
	• Upstaging
	• Change in nodal staging before and after surgery based upon Lymphoseek-identified nodes (and Lymphazurin, if applicable)
	• Number of changes in treatment plan and relation to lymph nodes identified by Lymphoseek
	Additionally for those subjects receiving both Lymphoseek and Lymphazurin:
	• Proportion of subjects with Lymphazurin-identified lymph nodes (i.e., localization)
	• Number of Lymphazurin-identified lymph nodes per subject (i.e., degree of localization)
	• Proportion of lymph nodes (and subjects) identified intraoperatively by Lymphazurin that are also identified intraoperatively by Lymphoseek (i.e., nodal and per-subject concordance)
	• Proportion of lymph nodes identified intraoperatively by Lymphoseek that are also identified intraoperatively by Lymphazurin control (i.e., nodal and per-subject reverse concordance)
	• Difference between nodal and reverse nodal concordance
Plan for statistical analysis	Analysis populations:
	• Safety: all enrolled subjects with administration of Lymphoseek
	• Intent-to-treat (ITT): all enrolled subjects with administration of Lymphoseek (with or without

Lymphazurin) and complete intraoperative lymphatic mapping
• Blue intent-to-treat (BITT): all ITT subjects with administration of Lymphazurin prior to ILM
• Per protocol (PP): all ITT subjects without major protocol violations
All safety analyses will be conducted on the safety population. The analysis of the diagnostic endpoints will be conducted on ITT, BITT, and PP populations, as applicable.
AEs will be summarized using system organ class and preferred term by tumor type and overall for all subjects in the safety population. AEs will also be summarized by severity, relationship to investigational product, and relationship to study procedure. All AEs will be listed.
Summary statistics (mean, median, sample size, standard deviation, minimum, and maximum) will be computed on the raw and change from baseline values for each vital sign parameter, quantitative laboratory parameter, and ECG parameter by time point, for each tumor type and overall.

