The localization rate, degree of localization, difference in preoperative SPECT versus intraoperative localization, agreement proportions of central pathology assessment to local pathology assessment, false negative rates, sensitivity rates, and upstaging, along with 95% confidence intervals, will be computed for each tracer (as applicable) for each tumor type and overall.
The proportion of ITT subjects with preoperative SPECT performed, those who had a hot spot on scan, and the time from Lymphoseek injection to hot spot localization, will be summarized by tumor type and overall.
Changes in nodal staging will be assessed via shift tables.
Changes in treatment plan and relation to lymph nodes will be listed.
Concordance endpoint analysis: For the BITT population, the number and proportion of concordant lymph nodes (Lymphoseek to Lymphazurin) will be computed, and a statistical test to determine if the concordance rate is greater than 0.9 will be conducted. In order for the test of the nodal concordance endpoint to successfully reject the null hypothesis that the concordance rate is ≤ 0.9 , the lower boundary of the one-sided 95% exact binomial confidence

interval must exceed 0.9 in the BITT population. In-house and/or literature data indicating that nodes may be considered as an independent sample will supplement the analysis.
If the test of the concordance endpoint is met (i.e., the null hypothesis is rejected), then a test for superiority of concordance relative to the secondary diagnostic endpoint of reverse concordance will be conducted using McNemar's test. If the one-sided p-value of the test is <0.05, then the concordance rate of Lymphoseek to Lymphazurin will be shown to be significantly greater than the reverse concordance rate of Lymphazurin to Lymphoseek.
The per-subject concordance and per-subject reverse concordance will also be computed along with 95% confidence intervals using the BITT population.
No formal interim analyses will be conducted during this study.
Data listings and tables will be created on an interim basis for review by a Data and Safety Monitoring Committee (DSMC), which is further described in Section 9.11.

TABLE OF CONTENTS

SY	NOPS	IS		2
LIS	ST OF	IN-TE2	XT TABLES	13
LIS	ST OF	APPEN	NDICES	13
LIS	ST OF	ABBR	EVIATIONS AND DEFINITIONS OF TERMS	14
TR	IAL A	DMIN	ISTRATIVE STRUCTURE	16
LA	BORA	ATORII	ES AND OTHER INSTITUTIONS FOR TRIAL CONDUCT	16
1	INT	RODU	CTION	17
	1.1	Back	ground	17

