9.6 Diagnostic Variables

9.6.1 Primary Diagnostic Variables

The primary diagnostic variables for this study are:

- Subject localization rate (defined as the proportion of subjects with Lymphoseekidentified lymph nodes)
- Number of lymph nodes identified intraoperatively by Lymphoseek per subject
- Proportion of subjects who underwent preoperative SPECT or SPECT/CT
- Proportion of subjects with a lymph nodes identified preoperatively using SPECT or SPECT/CT
- Number of lymph nodes identified preoperatively using SPECT or SPECT/CT
- Agreement of the number of nodes identified by preoperative SPECT or SPECT/CT to intraoperative localization
- Subject and nodal agreement of central pathology assessment with local pathology assessment of the excised lymph node(s) to confirm the presence/absence of tumor metastases
- Nodal false negative rate for Lymphoseek-identified nodes (using blinded central pathology assessment and local pathology assessment)
- Nodal sensitivity for Lymphoseek-identified nodes (using blinded central pathology assessment and local pathology assessment)
- Upstaging (defined as the proportion of patients with pathology-positive lymph nodes who had at least one pathology-positive lymph node that was identified by Lymphoseek and had no other pathology-positive lymph nodes [i.e., identified by any other method])
- Change in subject nodal staging before and after surgery based upon Lymphoseekidentified nodes
- Changes in treatment plan and relation to lymph nodes identified by Lymphoseek

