9.6.2 Secondary Diagnostic Variables

The secondary diagnostic variables for this study are for those subjects receiving both Lymphoseek and Lymphazurin:

- Subject localization rate for Lymphazurin
- Number of lymph nodes identified intraoperatively by Lymphazurin per subject
- Nodal concordance (defined as the proportion of lymph nodes identified intraoperatively by Lymphazurin that are also identified intraoperatively by Lymphoseek)
- Reverse nodal concordance (defined as the proportion of lymph nodes identified intraoperatively by Lymphoseek that are also identified intraoperatively by Lymphazurin)
- Subject concordance
- Subject reverse concordance
- Nodal false negative rate for Lymphazurin-identified nodes (using blinded central pathology assessment and local pathology assessment)
- Nodal sensitivity for Lymphazurin-identified nodes (using blinded central pathology assessment and local pathology assessment)

- Upstaging (defined as the proportion of patients with pathology-positive lymph nodes who had at least one pathology-positive lymph node that was identified by Lymphazurin and had no other pathology-positive lymph nodes (i.e., identified by any other method)
- Change in subject nodal staging before and after surgery based upon Lymphazurinidentified nodes

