9.9 Statistical Analysis

9.9.1 Analysis Populations

The following analysis populations will be defined:

Safety: The safety population will include all enrolled subjects with administration of Lymphoseek.

Intent-to-treat (ITT): The ITT population will include all protocol-eligible subjects with administration of Lymphoseek (with or without Lymphazurin) and complete intraoperative lymphatic mapping.

Blue intent-to-treat (BITT): The BITT population will include all ITT subjects who were also administered Lymphazurin prior to ILM.

Per protocol (PP): The PP population will include all ITT subjects without major protocol violations.

All safety analyses will be conducted on the safety population. The analysis of the diagnostic endpoints will be conducted on ITT, BITT, and PP populations, as applicable.

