9.9.5 Analysis of Primary Diagnostic Variables

The localization rate, defined as the proportion of ITT subjects that had at least one lymph node identified intraoperatively, along with a 95% confidence interval will be computed for Lymphoseek for each tumor type and overall.

The average number of lymph nodes identified intraoperatively by Lymphoseek per subject, along with a 95% confidence interval, will be computed for each tumor type and overall.

The proportion of ITT subjects who had preoperative SPECT performed will be summarized by tumor type and overall. The proportion of patients who had a hot spot on the scan will also be summarized by tumor type and overall. For those patients with a hot spot, the time from Lymphoseek injection to hot spot localization will be summarized.

The average number of lymph nodes identified with preoperative SPECT per subject, along with a 95% confidence interval, will be computed for Lymphoseek by tumor type and overall.

The average difference in the number of lymph nodes identified with preoperative SPECT per subject and the number of lymph nodes identified intraoperatively per subject, along with a 95% confidence interval, will also be computed.

The nodal and subject agreement of central pathology assessment to local pathology assessment will be computed as follows:

	Lymph nodes whose local and central pathology assessments were either	
Nodal	both positive or both negative	
Agreement =	Lymph nodes with non-missing local and central pathology results	

Where agreement on the subject level means that a subject either has at least one pathologypositive node with local and central pathology or has all pathology-negative nodes with local and central pathology. For the analysis of nodal agreement and subject agreement, only nodes that have non-missing local and central pathology results will be considered. Along with the agreement proportions, a 95% confidence interval will be computed for each endpoint. Subgroup analyses by tumor type will also be performed within the ITT and PP analysis populations.

The nodal false negative rate will be computed for Lymphoseek as the number of pathologypositive lymph nodes that were missed intraoperatively by the tracer divided by the total number of pathology-positive lymph nodes. A 95% confidence interval will also be computed. False negative rates also will be calculated separately for the blinded central pathology assessment and the local pathology assessment.

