The nodal sensitivity will be computed for Lymphoseek as the number of pathology-positive lymph nodes identified intraoperatively by the tracer divided by the total number of pathology-positive lymph nodes. A 95% confidence interval will also be computed. Sensitivities also will be calculated separately for the blinded central pathology assessment and the local pathology assessment.

The number and proportion of subjects upstaged by Lymphoseek will be computed along with a 95% confidence interval, where upstaging by an individual tracer is defined as a subject who had at least one pathology-positive node identified by one tracer and no pathology-positive nodes identified by the other tracer.

The change in subject nodal staging will be assessed via shift tables. A shift table for Lymphoseek will be produced to show the number of subjects with each combination of presurgery and post-surgery nodal staging. Each subject's post-surgery staging will be based on the pathology results of those nodes identified by Lymphoseek. For the purposes of this analysis, a subject may have two different post-surgery nodal staging results, one based on Lymphoseek-identified nodes and the other based on Lymphazurin-identified nodes (see Section 9.9.6).

Changes in treatment plan and relation to lymph nodes identified by Lymphoseek will be listed.

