The per-subject concordance, P_2 , and per-subject reverse concordance, P_4 , will be computed as follows using all subjects in the BITT population:

$$P_{2} = \frac{\begin{array}{c} \text{Subjects whose lymph nodes that were intraoperatively identified} \\ \text{Subjects with at least one lymph node intraoperatively identified by Lymphazurin} \end{array}}$$

and

$$P_{4} = \frac{\text{Subjects whose lymph nodes that were intraoperatively identified}}{\text{Subjects with at least one lymph node intraoperatively identified by Lymphoseek}}$$

In addition to the above proportions, exact one-sided 95% confidence intervals will be computed.

The nodal false negative rate will be computed for Lymphazurin as the number of pathologypositive lymph nodes that were missed intraoperatively by the tracer divided by the total number of pathology-positive lymph nodes. A 95% confidence interval will also be computed. False negative rates also will be calculated separately for the blinded central pathology assessment and the local pathology assessment.

The nodal sensitivity will be computed for Lymphazurin as the number of pathology-positive lymph nodes identified intraoperatively by the tracer divided by the total number of pathology-positive lymph nodes. A 95% confidence interval will also be computed. Sensitivities also will be calculated separately for the blinded central pathology assessment and the local pathology assessment.

The number and proportion of subjects upstaged by Lymphazurin will be computed along with a 95% confidence interval, where upstaging by an individual tracer is defined as a subject who had at least one pathology-positive node identified by one tracer and no pathology-positive nodes identified by the other tracer.

The change in subject nodal staging will be assessed via shift tables. A shift table for Lymphazurin will be produced to show the number of subjects with each combination of presurgery and post-surgery nodal staging. Each subject's post-surgery staging will be based on the pathology results of those nodes identified by Lymphazurin. For the purposes of this analysis, a subject may have two different post-surgery nodal staging results, one based on Lymphoseek-identified nodes and the other based on Lymphazurin-identified nodes.

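### The synopsis limits false negative rate and sensitivity to an undefined lymphadenectomy group; Section 9 uses all excised positive nodes, which biases Lymphoseek sensitivity upward by between zero and the true miss rate

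*Combined protocol and SAP*

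**What the plan says.** The endpoint list in the synopsis reads "False negative rates and sensitivity for each detection method in subjects undergoing lymphadenectomy". Lymphadenectomy is not defined there or elsewhere in the protocol.

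The synopsis paragraph on statistical analysis drops the restriction. Sections 9.6.1 and 9.6.2, which list the two measures for Lymphoseek and Lymphazurin, also omit it. So do the formulas. For the false negative rate (FNR), Section 9.9.5 says "The nodal false negative rate will be computed for Lymphoseek as the number of pathologypositive lymph nodes that were missed intraoperatively by the tracer". For sensitivity, the same section says "The nodal sensitivity will be computed for Lymphoseek as the number of pathology-positive lymph nodes identified intraoperatively by the tracer". Section 9.9.6 mirrors this for the dye: "The nodal false negative rate will be computed for Lymphazurin as the number of pathologypositive lymph nodes that were missed intraoperatively by the tracer". Each is divided by the total of pathology-positive nodes.

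On populations, Section 9.9.1 says "The analysis of the diagnostic endpoints will be conducted on ITT, BITT, and PP populations, as applicable". None of its four populations is defined by lymphadenectomy.

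**The concern.** There are two linked problems.

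First, the denominator is not settled. One analyst could follow the synopsis and another Section 9, and they could report different figures while both claiming to follow the protocol.

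Second, the Section 9 denominator depends partly on the agent under test. A positive node that is neither hot nor blue will often stay in the patient, never reach pathology and never be counted as missed. The result would still be labelled FNR or sensitivity. Its planned 95% confidence interval covers sampling error only. A reader could set a near-100% paediatric value beside the adult head and neck result in Section 1.2.3, where elective neck dissection was planned and non-sentinel nodes were also examined. The two figures would not measure the same thing.

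**Working it through.** **How a node enters the denominator.**
- Surgery removes the nodes found by mapping (synopsis, Methodology; Section 7.2.7).
- A sentinel node is one that is hot in vivo or blue, and probing stops once counts fall below threshold (Section 8.4.2).
- Subjects are clinically node negative at screening (Section 4.1.1), so grossly positive nodes should be uncommon.
- A non-hot node can still be removed because it is blue, through palpation or visualization, or as one of the discordant in vivo/ex vivo cases in Table 9. Dye is optional (Section 5.4).

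**Formula.** The documents give no target for FNR or sensitivity, so there is no planned figure to reproduce. Let s be the true nodal sensitivity of Lymphoseek, b the chance that a positive node is blue, and q the chance that a positive node neither hot nor blue is removed anyway. With hot and blue status independent,

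reported sensitivity = s / [1 − (1 − s)(1 − b)(1 − q)].

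If q = 1, the reported value is s and the bias is 0. If b = 0 and q = 0, the reported value is s/s = 100% and the bias is 1 − s, which is its maximum.

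**Inputs, all adult data used as assumptions.**
- s = 99.99%: per-node Phase 3 meta-analysis (Section 1.2.3).
- s = 38/39 = 97.4%: Phase 3 head and neck trial, per subject (Section 1.2.3; 1/39 = 2.56%, matching the stated FNR).
- s = 92.0%: Phase 2, per tissue (Section 1.2.2).
- b = 0.7802 where dye is given (Section 1.2.3). With dye in half the subjects, b = 0.3901.
- q = 0 in the table, meaning no capture by palpation or visualization.

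Example, s = 92.0% with dye in all: 0.92 / (1 − 0.08 × 0.2198) = 0.92 / 0.98242 = 0.9365, a bias of 1.6 points (1.647 before rounding).

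| True s | No dye | Dye in half | Dye in all |
|---|---|---|---|
| 99.99% | 100% (+0.01) | under +0.01 | under +0.01 |
| 97.4% | 100% (+2.6) | 99.0% (+1.5) | 98.0% (+0.6) |
| 92.0% | 100% (+8.0) | 96.7% (+4.7) | 93.6% (+1.6) |

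Bias in points is taken before rounding. Some capture by other routes lowers it. With no dye and q = 0.10, s = 92.0% reads 99.1% (+7.1) and s = 97.4% reads 99.7% (+2.3). With q = 0.50 they read 95.8% (+3.8) and 98.7% (+1.3).

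**Number of positive cases.** Section 1.1 gives node-positive rates of 21.4% (6/28, rhabdomyosarcoma) and 25.6% (paediatric melanoma). Applied to all 27 subjects, and assumed to hold for the other tumors too: 27 × 0.214 = 5.8 and 27 × 0.256 = 6.9, so about 6 to 7 subjects. If each has one positive node and all are hot, the exact 95% lower limit is 0.025^(1/6) = 54.1% or 0.025^(1/7) = 59.0%.

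**The case against.** **The texts may not contradict each other.** Because lymphadenectomy is undefined, a firm contradiction is only one reading. Two cited titles, one on breast cancer and one on prostate cancer, use the word for sentinel-node removal, and the background sections say dissection when they mean fuller removal. On that reading the synopsis and Section 9 cover nearly the same subjects, since those without mapping and node biopsy are replaced (Section 4.4). This stands: the phrase is ambiguous. It does not settle the denominator, and on that reading the selection of nodes remains in full.

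**The bias may be trivial.** At the documents' own nodal Phase 3 value of 99.99% it cannot exceed 0.01 point. That is a fair scenario and is in the table. However, the documents do not say that the nodes behind 99.99% or 92.0% were verified by full dissection, so those inputs may carry the same selection.

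**There is already a check on Lymphoseek misses.** Nodal concordance uses blue nodes as its denominator, so Lymphoseek does not select it, and it is tested against 0.9. This is useful, but it covers dye subjects only and all blue nodes rather than positive ones.

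**Stronger readings a reader might infer.**
- *That sensitivity must come out at 100%.* This holds only where no dye is used and no non-hot node is removed. Section 8.4.2 calls for palpation and visualization, so it is a limiting case.
- *That the bias is 20 points or more.* That needs a true sensitivity of 80% or lower, for which the documents give no source.
- *That a trial conclusion depends on it.* No hypothesis test uses FNR or sensitivity, and the primary objective is safety (Section 2.1).

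**Conclusion.** The point holds as a problem of denominator and label. The protocol does not state consistently who is in the FNR and sensitivity analysis. Followed as written, Section 9 yields a Lymphoseek sensitivity biased upward, and an FNR biased downward, by between 0 and 1 − s. The exact amount cannot be fixed, because s, the share of subjects given dye and the frequency of other removals are not in the documents.

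The sizes in the table rest on adult figures, one of them per subject, and on independence of hot and blue status. With so few positive cases, sampling error may well be larger than the bias. FNR and sensitivity appear as two of the twelve primary diagnostic variables but are complements of each other, so one quantity is affected. Severity is minor to moderate.

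This covers the synopsis and Section 9. The separate statistical analysis plan that Sections 9.9.4 and 9.9.6 mention was not available and may already address the matter.

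**What to change.** 1. Reconcile the synopsis endpoint list with the synopsis analysis paragraph and Sections 9.6.1, 9.6.2, 9.9.1, 9.9.5 and 9.9.6. State what lymphadenectomy means for the analysis and which subjects form the FNR and sensitivity denominator, and report how many there are.
2. Label any figure computed on all excised positive nodes *detection among excised pathology-positive nodes*, not FNR or sensitivity. Add that nodes neither hot nor blue are largely unverified.
3. Tabulate excised pathology-positive nodes by hot/blue status, separately for subjects with and without Lymphazurin, using the identification method already recorded per node (Section 8.4.2, step 6). In dye subjects, also report the share of blue pathology-positive nodes that were hot. Note that positive dependence between hot and blue status would leave that share too high as an estimate of s.

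The cost is some wording, one extra table from data already collected, and a less favourable label or figure. If the reconciled definition is narrow, the denominator will be small and could be empty; reporting its size makes that visible. No change to surgery is proposed.

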1 INTRODUCTION

1.1 Background

Intraoperative Lymphatic Mapping (ILM) and Sentinel Lymph Node Biopsy (SLNB) in Adult Cancer Patients

In patients with malignant melanoma and breast cancer, lymph node status is often a strong predictor of outcome and influences the course of treatment a patient may follow after surgery. In an effort to reduce the morbidity and cost of detecting lymph node metastases, surgical oncologists have developed a method by which the sentinel lymph node(s) (SLN); i.e., the first node or nodes in a draining basin), which have the highest probability of harboring cancer, is/are identified intraoperatively and removed. This technique, called ILM with SLNB, has extremely high negative predictive values for both melanoma (Morton et al., 2006) and breast cancer (Giuliano et al., 1994) metastases. The two largest trials for melanoma (Morton et al., 2005 and Rossi et al., 2006), reported false negative rates of 6.3% and 14.7%, respectively. Morton et al. (2006) showed a false negative rate of 3.4%. SLNB has also been evaluated with positive results in adult patients being surgically treated for head and neck squamous cell carcinoma (Thompson et al., 2012; Stoeckli, 2007; Melkane et al., 2012; Broglie et al., 2011; Marcinow et al., 2013), colon cancer (Dionigi et al., 2007; van der Zaag et al., 2012), prostate cancer (Ponholzer et al., 2012), cervical cancer (Gortzak-Uzan et al., 2010; Bats et al., 2012), and lung cancer (Taghizadeh et al., 2013).

During an ILM procedure with SLNB, a radioactive tracing agent such as Lymphoseek, is injected at the site of the primary tumor and follows the drainage path of the tumor to the nearest lymph node(s). After injection of the radioactive agent, external scintigraphic imaging (i.e., lymphoscintigraphy or preoperative single photon emission computed tomography [SPECT]) can be performed to assist in the preoperative localization of nodes. A handheld gamma detection device is then used to track the pathway of the tracing agent.

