1.2.3 Clinical Efficacy

Clinical efficacy was evaluated in two pivotal Phase 3 clinical trials in adult subjects with breast cancer and melanoma, comparing lymph node detection of Lymphoseek and VBD. Lymphoseek demonstrated a statistically significant concordance rate with VBD (meta-analysis concordance rate = 99.99%).

The detection concordance between Lymphoseek and VBD was similar among subjects with melanoma and subjects with breast cancer (meta-analysis concordance rate = 99.99% for both populations). Lymphoseek also demonstrated a higher sensitivity for detecting tumor-positive (as confirmed by pathology) lymph nodes, corresponding to a decreased FNR when compared with VBD on a per node basis. The corresponding sensitivity rate in detection of lymph nodes most likely to be positive for tumor cells for Lymphoseek was 99.99%, compared with 78.02% for VBD. The FNR for VBD (21.98%) was higher than the FNR for Lymphoseek (0.01%). These findings suggest that, when VBD is used as the imaging agent, there is an increased risk of missing the detection of tumor-involved lymph nodes and incorrectly staging cancer patients. The Lymphoseek-only findings (pathology-positive nodes

that were hot/not blue) suggest that Lymphoseek was markedly more effective in identifying lymph nodes that harbored disease than was VBD.

A third pivotal Phase 3 clinical trial was conducted in adult subjects with oral cavity or cutaneous SCC. Subjects received an injection of Lymphoseek prior to surgery for excision of the primary tumor and Lymphoseek-guided SLN dissection followed by planned elective neck dissection. All excised lymph nodes (Lymphoseek-identified SLNs as well as non-SLNs) underwent histopathologic evaluation for presence of metastatic disease. The primary endpoint in this trial was the Lymphoseek FNR (subjects with pathology-positive lymph node(s) not identified by Lymphoseek). Thirty-nine subjects had at least one pathology-positive lymph node, and Lymphoseek detected nodes with positive pathology in all but one patient. The FNR in this trial was 2.56%.

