Table 9 describes the procedures that should be followed based on the in vivo and ex vivo status of the tissue that has been excised.

Table 9.	Handling of Excise	d Tissue
----------	--------------------	----------

In Vivo Assessment	Ex Vivo Assessment	Procedure		
Radioactive Status	Radioactive Status			
positive (hot)	positive (hot)	Send to pathology for further evaluation.		
positive (hot)	negative (not hot) or no counts obtained	Incorrect node harvested. Send to pathology for further evaluation. Return to resection bed.		
negative or no counts (not hot)	positive (hot)	Comment on why lymph node was removed. Send to pathology for further evaluation.		
Vital Blue Dye Status				
Blue node	N/A	ANY blue node is sent to pathology for further evaluation regardless of radioactive status.		

- 8. A thorough evaluation of the remaining lymphatic basin should be undertaken since more than one LN may be found. This evaluation should include a combination of palpation, visualization, and gamma detector survey for evidence of blue and/or increased gamma detector count rates.
- 9. Probing of the area will be complete when all selected node counts are negative by use of the threshold criterion. The surgeon will continue with visualization and palpation according to local practice to ensure that no grossly positive LNs remain at the site of resection.

If a subject has neither a blue node nor any "hot" nodes, continue with visualization and palpation according to your medical expertise.

All removed LNs must be sent to pathology for further evaluation. The pathological evaluation of lymph node(s) will include serial sectioning and staining as described below (see also the Pathology Manual for additional details). For the purposes of analysis, a sentinel lymph node is defined as either being hot in vivo (lymph nodes with counts above the 3σ rule threshold) or blue (when applicable).

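### False negative rate and sensitivity are defined per node only; a subject-level version should stand beside them, so that the share of node-positive children missed is reported

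*Combined protocol and SAP*

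**What the plan says.** The variable list in Section 9.6.1 names "Nodal false negative rate for Lymphoseek-identified nodes (using blinded central pathology assessment and local pathology assessment", with a matching nodal sensitivity. Section 9.6.2 does the same for Lymphazurin. The computations follow in 9.9.5 ("The nodal false negative rate will be computed for Lymphoseek as the number of pathologypositive lymph nodes that were missed intraoperatively by the tracer" and "The nodal sensitivity will be computed for Lymphoseek as the number of pathology-positive lymph nodes identified intraoperatively by the tracer") and in 9.9.6 ("The nodal false negative rate will be computed for Lymphazurin"). Each is divided by all pathology-positive nodes and gets a 95% interval of unstated type.

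The denominator is not limited to sentinel nodes. Section 8.4.2 states that "All removed LNs must be sent to pathology for further evaluation", so a positive node that was neither hot nor blue enters it.

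The synopsis words the endpoint differently: "False negative rates and sensitivity for each detection method in subjects undergoing lymphadenectomy". It gives no unit, and it carries a restriction that Section 9 does not repeat.

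Localization, concordance and central-to-local pathology agreement all have subject-level versions. Section 1.2.3 describes the third Phase 3 trial thus: "The primary endpoint in this trial was the Lymphoseek FNR (subjects with pathology-positive lymph node(s) not identified by Lymphoseek". That is a per-subject rate.

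The protocol defers some details to a separate statistical analysis plan. The text in hand contains no analysis wording beyond Section 9.

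**The concern.** A nodal rate and a subject rate answer different questions. The nodal rate asks what share of positive nodes the tracer marked. The subject rate asks in what share of node-positive children it marked no positive node. The second bears directly on whether a child is recognized as node-positive, and the secondary objectives include change of stage and of treatment plan for the subject.

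With very few node-positive children, the nodal rate is driven by how many positive nodes each child happens to have. It can look poor when no child was missed, or good when one was. If only the nodal rate is prespecified, the unit for any statement about children would be chosen after the data are known.

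**Working it through.** **Inputs**
- Planned enrollment: 6 melanoma + 6 rhabdomyosarcoma + up to 15 other = 27 (9.7).
- Node positivity at sentinel node biopsy, from 1.1: rhabdomyosarcoma 6/28 = 21.4%; melanoma 25.6%. A dissection series in rhabdomyosarcoma gives 14%.
- Third Phase 3 trial: 39 node-positive subjects, one missed (1.2.3).
- Node counts per child: not in the documents, so assumed below.

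**The cited figure.** 1/39 = 2.56%, which reproduces (exact 95% CI 0.06% to 13.5%). The present plan states no target, hypothesis or power for false negative rate or sensitivity, so there is no planned figure to reproduce.

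**Expected node-positive children**
- All 27, if the cited rates also hold for other tumors: 27 × 0.214 = 5.8; 27 × 0.256 = 6.9.
- All 27 at 14%: 27 × 0.14 = 3.8.
- The 12 guaranteed subjects only: 6 × 0.214 + 6 × 0.256 = 1.28 + 1.54 = 2.8.

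**How far the two rates can part (6 node-positive children, assumed)**

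*A. No child missed.* Each child has one hot positive node, and one child also has k cold positive nodes. Nodal rate = k/(6 + k); subject rate = 0/6.

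| k | Nodal | Subject |
|---|---|---|
| 1 | 1/7 = 14.3% | 0% |
| 2 | 2/8 = 25.0% | 0% |
| 3 | 3/9 = 33.3% | 0% |
| 4 | 4/10 = 40.0% | 0% |

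*B. One child missed.* One child's only positive node is cold, and the other five have m hot positive nodes each. Nodal rate = 1/(5m + 1); subject rate = 1/6.

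| m | Nodal | Subject |
|---|---|---|
| 1 | 1/6 = 16.7% | 16.7% |
| 2 | 1/11 = 9.1% | 16.7% |
| 3 | 1/16 = 6.3% | 16.7% |

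**Do other planned outputs count the missed children?** Take a child with positive nodes, none of them hot.
- Dye given, a positive node was blue: counted in upstaging by Lymphazurin (9.9.6).
- Dye given, positive nodes neither hot nor blue: not counted.
- No dye given: not counted.

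The Lymphoseek shift table (9.9.5) stages on Lymphoseek-identified nodes only. A missed child whose hot nodes were negative appears there as N0, like a child with no metastasis.

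**Precision of a subject-level rate (exact 95%).** With no child missed, the upper limit is 1 − 0.025^(1/n): 0/6 gives 46% and 0/7 gives 41%. With one missed, 1/6 = 16.7% (0.4% to 64.1%) and 1/7 = 14.3% (0.4% to 57.9%).

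**The case against.** **The nodal rate has a proper use.** A reader might infer that every cold positive node is a spurious miss in a child who was staged correctly. The documents do not support that. In Table 6 the melanoma N category depends on the number of positive nodes (N1 for one, N2 for two or three, N3 for four or more), so a cold second node can leave a child under-staged. In Table 5, rhabdomyosarcoma Group II(c) refers to involvement of the most distal node. The background defines a sentinel node as "the first node or nodes in a draining basin", but nowhere says that the tracer should be excused for positive nodes further along.

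**There is precedent for it.** Section 1.2.3 reports the pooled breast and melanoma Phase 3 results per node (0.01% against 21.98%), and 1.2.2 gives a Phase 2 per-tissue sensitivity of 92.0%. The per-subject 2.56% is one precedent among several.

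**Missed children are not wholly unreported.** A reader might infer that the plan never counts them. Upstaging by Lymphazurin does so, with an interval, for part of the dye-treated subset.

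**A subject-level rate has its own bias.** The trial behind the 2.56% included planned elective neck dissection. Here subjects are clinically node negative, probing ends when counts fall below threshold, and a cold node is likely to come out mainly if it is blue, visible or palpable. Misses can be seen only where non-hot nodes were removed, so a rate over all node-positive children may lean toward zero and is not directly comparable with 2.56%.

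**The stakes are modest.** Safety is the primary objective, and no decision rests on these rates.

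All five points stand. They argue against replacing the nodal rate or demoting it, but not against reporting the subject-level rate beside it.

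**Conclusion.** The gap is real but limited. As written, Section 9 gives no full count of node-positive children in whom Lymphoseek identified no positive node, and the nodal rate cannot stand in for that count. In the illustrative cases it is 40% against 0% in one direction and 6.3% against 16.7% in the other.

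Those figures rest on assumed node counts and show the mechanism, not a forecast. The 6 to 7 node-positive children rest on applying melanoma and rhabdomyosarcoma rates to up to 15 children with other tumors, for whom the documents give none.

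Making the subject-level rate the principal one would be a preference that the documents do not compel. Adding it is a cheap improvement.

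**What to change.** - In 9.6.1 and 9.6.2, and in 9.9.5 and 9.9.6, add a subject-level false negative rate: node-positive subjects in whom the tracer identified no pathology-positive node, divided by all node-positive subjects. Add its complement, sensitivity. Give exact 95% intervals, for each tracer, by central and by local pathology.
- Keep the nodal rates and report both side by side.
- Reconcile Section 9 with the synopsis restriction to lymphadenectomy. Report the subject-level rate in that subset and in all node-positive subjects, noting that the all-subject rate may be biased toward zero because misses show only where non-hot nodes were removed.

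The cost is a change of wording and one or two extra table rows per tracer, from data already collected. The downside is wide intervals, which should be shown as they are.
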